15.1.4. Sensitivity Analysis of Primary Efficacy Variable(s)

Sensitivity analysis of primary efficacy variable will be based on observed data and the analysis will be conducted by using the same ANCOVA model mentioned above with observed seDBP only.

7.0 Document: 2014-000674-18 Statistical Analysis Plan Version 7.0 Version Number:

Version Date:

13JAN2020

Template No.: CS_TP_BS016 Revision 5 Reference: CS_WI_BS005

Effective Date: 01Apr2018

Author:

15.2. SECONDARY EFFICACY

The secondary efficacy analyses will be performed for the FAS.

15.2.1. Secondary Efficacy Variables & Derivations

15.2.1.1.

Change from Week 6/Final Visit of the DB Phase to Week 8/Final Visit of the Withdrawal Phase in trough clinic seSBP and MAP between AZM and placebo.

Clinic seSBP and seDBP are collected from eCRF and MAP is calculated as following.

MAP = seSBP + 2 (seDBP)3

15.2.1.2.

Change from baseline in trough clinic seDBP, seSBP, and MAP at Week 6/Final Visit for AZM and losartan. Clinic seDBP and seSBP are collected from eCRF and MAP is calculated using formula mentioned above.

15.2.1.3.

Percentage of subjects who achieve target BP (seDBP, seSBP, both) at Week 8/Final Visit of the Withdrawal Phase, with the target defined as <90th percentile for age, gender, and height.

15.2.2. MISSING DATA METHODS FOR SECONDARY EFFICACY VARIABLE(S)

15.2.2.1.

The same multiple imputations for missing data as primary endpoint (Section 15.1.2) will be used for Change from Week 6/Final Visit of the DB Phase to Week 8/Final Visit of the Withdrawal Phase in trough clinic seSBP and MAP.

15.2.2.2.

For change from baseline in trough clinic seDBP, seSBP, and MAP to Week 6/Final Visit, last observation carried forward (LOCF) method for missing data will be used for the sensitivity analysis. In the LOCF analysis data set, the last post baseline double-blind observed value will be carried forward and used for all subsequent scheduled time points in the DB Phase where data are missing (e.g., the subject has missing data or has dropped out of the study).

15.2.2.3.

For analysis of percentage of subjects who achieve target BP at Week 8/Final Visit of the Withdrawal Phase will be based on LOCF. Sensitivity analysis will be done using multiple imputation

2014-000674-18 Statistical Analysis Plan Version 7.0 7.0 Document: Version Number: Author: Version Date: 13JAN2020

Template No.: CS_TP_BS016 Revision 5 Reference: CS_WI_BS005

Effective Date: 01Apr2018

15.2.3. Analysis of Secondary Efficacy Variables

15.2.3.1.

Change from Week 6/Final Visit of the DB Phase to Week 8/Final Visit of the Withdrawal Phase in trough clinic seSBP and MAP will be analyzed using an ANCOVA model with treatment (AZM low, med, high and placebo), age (Tanner stage <3, ≥3), race (Black or African American, Non- Black or African American) and weight (<50 kg, ≥50 kg) as fixed effects, and baseline value (seDBP or MAP) as a covariate. The comparison, mean (i.e., pooled) AZM effect versus placebo, will be made using an ANCOVA contrast statement. Comparisons between each AZM dose to placebo will also be done from the framework of the above ANCOVA using contrast statements.

This analysis will exclude subjects that were treated with losartan during the DB Phase. There will be no sequential testing procedure for this analysis.

Profile plots (line with symbol at each visit with +/- 1 SE error bars) will be displayed for observed seSBP and MAP and boxplot will be displayed for the change in seSBP and MAP from Week 6 to Week 8.

15.2.3.2.

Change from baseline in trough clinic seDBP, seSBP, and MAP at Week 6/Final Visit, will be analyzed with a mixed models for repeated measure (MMRM) with treatment (AZM low, med, high dose and losartan), time point (Week 2, Week 4, Week 6), treatment by time interaction, age (Tanner stage <3, ≥3), race (Black or African American, Non- Black or African American) and weight (<50 kg, ≥50 kg) as fixed effects, and corresponding baseline value (seDBP, seSBP, MAP) as a covariate. An unstructured covariance matrix will be used to model the within-subject variation-covariance errors. The comparison, mean (i.e., pooled) AZM effect versus losartan, will be made using contrast statement. Comparisons between each AZM dose to losartan will be done from the framework of the above MMRM. Observed data will be used to perform MMRM. Sensitivity analyses will be performed including ANCOVA at each time point using last observation carried forward (LOCF).

In case of non-convergence, the following tests in sequence will be used: heterogeneous Toeplitz covariance structure, heterogeneous autoregressive covariance structure, heterogeneous compound symmetry covariance structure.

Profile plots (line with symbol at each visit with +/- 1 SE error bars) will be displayed for the change in seDBP, seSBP and seMAP from baseline to Week 6.

15.2.3.3.

The analysis of subject who achieves target BP (seDBP, seSBP, both) at Week 8/Final Visit of the Withdrawal Phase, with the target defined as <90th percentile for age, gender, and height, will be conducted using logistic models with treatment (AZM low, med, high and placebo), age (Tanner stage <3, ≥3), race (Black or African American, Non- Black or African American)and weight (<50 kg, ≥50 kg) as fixed effects and baseline clinic seated BP as a covariate. The analysis will be based on LOCF data. Sensitivity analysis will be done using multiple imputation. The number and percentage of subjects who achieved target BP at Week 8/Final Visit of the Withdrawal Phase will be presented, along with the odds ratios and associated 95% CIs. Percentage will be calculated as:

Number of subjects with target blood pressure / Number of subjects with BP at week 8Profile plots (line with

Document: 2014-000674-18 Statistical Analysis Plan Version 7.0 Version Number: 7.0

Author: Version Date: 13JAN2020

Template No.: CS_TP_BS016 Revision 5 Reference: CS_WI_BS005

Effective Date: 01Apr2018

symbol at each visit with +/- 1 SE error bars) will be displayed for the change in seDBP, seSBP and seMAP from baseline to Week 8.

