5.2.2 Secondary Endpoints

- Change from Week 6/Final Visit of the DB Phase to Week 8/Final Visit of the Withdrawal Phase in trough clinic seated systolic blood pressure (seSBP) and mean arterial pressure (MAP) between AZM and placebo.
- Change from Baseline in trough clinic seDBP, seSBP, and MAP at Week 6/Final Visit for AZM and losartan.
- Percentage of subjects who achieve target BP (seDBP, seSBP, both) at Week 8/Final Visit of the Withdrawal Phase, with the target defined as <90th percentile for age, gender, and height.

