Secondary endpoints, change from Week 6/Final Visit of the DB Phase to Week 8/Final Visit of the Withdrawal Phase for clinic seSBP and MAP, will be analyzed using an ANCOVA model and contrast statements similar to what was used for the primary endpoint analysis, except the relevant baseline covariate term will be used in the analysis. These analyses will be performed without using the sequential testing procedure.

The analysis for the secondary endpoint, change from baseline to Week 6/Final Visit of the DB Phase, will be mixed models for repeated measure (MMRM) with treatment (AZM low, med, high dose and losartan), age (Tanner stage <3, ≥ 3) and weight (<50 kg, ≥ 50 kg) as fixed effects, and baseline seDBP as covariate. An unstructured covariance matrix will be used to model the within-subject variation-covariance errors. The primary comparison, mean (ie, pooled) AZM effect versus losartan, will be made using contrast statement. Comparisons between each AZM dose to losartan will be done from the framework of the above MMRM. Additional sensitivity

analyses will be performed including ANCOVA using observed case data and last observation carried forward (LOCF). Similar analyses will be performed for the secondary endpoints change from baseline in seSBP and MAP at Week 6/Final Visit of the DB Phase and each other visit of the DB Phase. Additional analyses, e.g. similar MMRM models with different factors, for the above endpoints may be performed where appropriate.

Exploratory dose response analysis using only AZM low, med and high dose groups, for change from Baseline to Week 6/ Final Visit of the DB Phase in clinic seDBP will be performed using linear regression model with weight adjusted dose (mg/kg) as the continuous covariate.

Additionally, an ANCOVA with treatment, age and weight as fixed effects, and baseline seDBP as covariate will be performed to assess between-group comparisons. Similar analyses may be performed on change from Baseline in seSBP and MAP at Week 6/Final Visit of the DB Phase and each other visit of the DB Phase.

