6.3. ENDPOINTS

The primary endpoint for this study is

Change from Week 6/Final Visit of the DB Phase to Week 8/Final Visit of the Withdrawal Phase in trough clinic seDBP between AZM and placebo.

Secondary endpoints for this study are:

- Change from Week 6/Final Visit of the DB Phase to Week 8/ Final Visit of the Withdrawal Phase in trough clinic seDBP and mean arterial pressure (MAP) between AZM and placebo.
- Change from baseline in trough clinic seDBP, seated systolic blood pressure (seSBP), and MAP to Week 6/Final Visit of the DB Phase for AZM and losartan.
- Percentage of subjects who achieve target BP (seDBP, seSBP, both) at Week 8/Final Visit of the Withdrawal Phase, with the target defined as <90th percentile for age, gender, and height.

Safety Endpoints for this study are:

- Adverse events (AEs).
- Physical examination.
- Laboratory tests.
- 12-lead electrocardiogram (ECG) finding.
- Vital signs.
- Anthropometric (height, weight, and body mass index z-scores) measurements.

Additional Endpoints for this study are:

- Change from baseline in trough clinic seDBP, seSBP and MAP at all visits of the DB Phase, excluding the Week 6/Final Visit for AZM and losartan.
- Change from baseline in trough clinic seDBP, seSBP and MAP at all visits of the OL Phase, including Week 52/Final Visit.
- Percentage of subjects who achieve the following additional BP targets (for seSBP, seDBP and both):
- All Subjects:
 - <90th percentile at Week 6/Final Visit of the DB Phase and Week 52/Final Visit of the OL Phase
 - in subjects with chronic kidney disease (CKD).
 - <90th percentile at Weeks 6, 8, and 52/Final Visits of the DB Phase, Withdrawal Phase, and OL Phase, respectively.
 - <50th percentile at Weeks 6, 8, and 52/Final Visits of the DB Phase, Withdrawal Phase, and OL Phase, respectively.
 - Estimation of the exposure using population pharmacokinetics of azilsartan.

Exploratory Endpoints are:

- Change from baseline to Week 6/Final Visit of the DB Phase and to Week 52/Final Visit of the OL Phase in 24-hour, 12-hour, daytime, night time, and trough DBP and SBP by ABPM.
- AZM dose response for change from baseline to Week 6/Final Visit of the DB Phase in clinic seDBP and seSBP.

2014-000674-18 Statistical Analysis Plan Version 7.0 7.0 Document: Version Number: Author: Version Date: 13JAN2020

Template No.: CS_TP_BS016 Revision 5 Reference: CS_WI_BS005

Effective Date: 01Apr2018

RETESTS, UNSCHEDULED VISITS AND EARLY TERMINATION DATA

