7. STATISTICAL CONSIDERATIONS

7.1. ADJUSTMENTS FOR COVARIATES AND FACTORS TO BE INCLUDED IN ANALYSES

The following covariates and factors are used in the analyses. For details of their inclusion in the models, see the specific analysis section.

- Week 6/Final Visit of the DB Phase seDBP.
- Baseline seDBP.
- Baseline seSBP.
- Baseline MAP.
- Treatment during DB Phase (AZM low, med, high dose and losartan).
- Treatment during Withdrawal Phase, (AZM low, med, high and placebo).
- Treatment for study drug (AZM low, med, high).
- Age (Tanner stage $<3, \ge 3$).
- Weight (<50 kg, ≥50 kg).
- Race Group (Black or African American, Non- Black or African American).

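### SAP 15.2.3.1 adjusts the Week 6 to Week 8 change in seated systolic pressure for diastolic pressure, contrary to protocol 13.1.3

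*SAP*

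**What the plan says.** Protocol 5.2.2 lists as its first secondary endpoint the Withdrawal-Phase change in "trough clinic seated systolic blood pressure (seSBP) and mean arterial pressure (MAP) between AZM and placebo". Protocol 13.1.3 says these two outcomes get an ANCOVA like the primary one, "except the relevant baseline covariate term will be used in the analysis". The primary model adjusts the change in seDBP for Week 6 seDBP, which is the outcome's own starting value.

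The SAP is not consistent with this, or with itself:

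- 15.2.1.1 has the endpoint right: "trough clinic seSBP and MAP between AZM and placebo".
- 15.2.3.1 names seSBP and MAP as the outcomes, then gives the model terms "as fixed effects, and baseline value (seDBP or MAP) as a covariate".
- 15.2.3.2, the next model, uses the "corresponding baseline value (seDBP, seSBP, MAP) as a covariate".
- 6.3 defines the first secondary endpoint as the change in "trough clinic seDBP and mean arterial pressure (MAP) between AZM and placebo". That repeats the primary endpoint and omits seSBP.
- 7.1 lists "Baseline seSBP" among the covariates but sends the reader to the specific analysis section for how it is used. The only Week 6 covariate it lists is "Week 6/Final Visit of the DB Phase seDBP".
- 3.6, on changes from the protocol, points only to the sample size section.

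**The concern.** An ANCOVA on a change score gains most of its precision from the outcome's own starting value. That value also corrects the comparison when the groups happen to differ at the start. If systolic change is adjusted for diastolic pressure, much of that gain may be lost in a named secondary endpoint.

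A programmer could follow the wrong text without noticing. The endpoint list in 6.3 and the covariate in 15.2.3.1 carry the same substitution, so they appear to support each other. The list in 7.1 does not settle the matter, because it defers to 15.2.3.1.

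The visit also needs naming. Section 6.2 defines baseline by default as the last value before first dose, Appendix 1 makes Week 6 the Withdrawal-Phase baseline, and 15.2.3.1 says only baseline.

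**Working it through.** **Text.** The outcomes in 15.2.3.1 are seSBP and MAP, and the covariates named are seDBP and MAP. seDBP is not an outcome of this model, and the seSBP outcome has no covariate of its own. Protocol 13.1.3, the primary model and SAP 15.2.3.2 all match covariate to outcome. No departure is declared in 3.6. The text is therefore wrong as written.

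**Size.** The plan has no figure to reproduce and gives no correlations, so what follows is an illustration. Assume unit variance of seSBP and seDBP at each visit, and ignore the weight, Tanner and race terms. Let

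- ρ = correlation of Week 6 seSBP with Week 8 seSBP
- r = correlation of Week 6 seSBP with Week 6 seDBP
- c = correlation of Week 6 seDBP with Week 8 seSBP

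Residual variance of the seSBP change:

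- adjusted for Week 6 seSBP: 1 − ρ²
- adjusted for Week 6 seDBP: 2(1 − ρ) − (r − c)²

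Share of the effect of a chance Week 6 seSBP imbalance that remains after adjusting for seDBP: 1 − (r − c)r/(1 − ρ).

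| ρ, r, c | Variance, seDBP / seSBP | Ratio | Share left |
|---|---|---|---|
| 0.5, 0.5, 0.25 | 0.9375 / 0.75 | 1.25 | 0.75 |
| 0.5, 0.5, 0.10 | 0.84 / 0.75 | 1.12 | 0.60 |
| 0.5, 0.5, 0.40 | 0.99 / 0.75 | 1.32 | 0.90 |
| 0.7, 0.5, 0.35 | 0.5775 / 0.51 | 1.13 | 0.75 |
| 0.7, 0.5, 0.25 | 0.5375 / 0.51 | 1.05 | 0.58 |
| 0.7, 0.5, 0.45 | 0.5975 / 0.51 | 1.17 | 0.92 |
| 0.8, 0.8, 0.64 | 0.3744 / 0.36 | 1.04 | 0.36 |
| 0.8, 0.8, 0.54 | 0.3324 / 0.36 | 0.92 | −0.04 |

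The standard error grows by the square root of the ratio: √1.25 = 1.12 and √1.13 = 1.06.

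A second grid set c = ρr, so that diastolic pressure predicts Week 8 systolic pressure only through Week 6 systolic pressure. With ρ from 0.5 to 0.7 and r from 0.4 to 0.7, the variance rises by 9% to 28% and the standard error by 4% to 13%.

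**Scale.** Subjects in the AZM arms with data: 213 × 3/4 × 0.9 = 144, or 72 per comparison group. With the wrong covariate they carry the information of 144/1.25 = 115 subjects in the first case, and of 144/1.13 = 127 in the fourth.

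**Bias.** In 6,000 simulated trials with n = 144 and no true effect, the mean estimated effect was 0.00 with either covariate. The variance ratios were 1.26 at (0.5, 0.5, 0.25) and 1.13 at (0.7, 0.5, 0.35), in line with the formulas.

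**The case against.** The strongest reply is that this is a typing error whose meaning can be recovered, and that the SAP's own code points to the right model. Section 15.2.2.1 applies the primary endpoint's multiple imputation to seSBP and MAP. Appendix 5, which sets out that procedure, regresses the change on the Week 6 value of the same variable. Run on seSBP, the template would adjust for Week 6 seSBP. This is good evidence of intent. But 15.2.2.1 imports only the missing-data method, Appendix 5 labels its scores as seDBP, and nothing there overrides 15.2.3.1.

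On the visit, 6.2 allows exceptions and Appendix 1 supplies one, so Week 6 is the better reading. That largely holds. Naming Week 6 is a clarification and does not repair a contradiction.

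On size, every correlation is assumed, and the results run from 32% more variance to 8% less. The formula also assumes equal variances and omits the other model terms. This stands. The lower central figure, 13%, may be the more realistic one, because each visit value averages three readings. The size therefore cannot carry the point by itself; the conflict with the protocol does.

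**Conclusion.** The point holds and should be fixed. As written, SAP 15.2.3.1 specifies a covariate for the systolic analysis that departs from protocol 13.1.3, and the departure is not declared. The conclusion rests on the text alone.

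The consequences are limited. There is no bias, no effect on the primary analysis, and no type I error consequence, since protocol 13.1.3 places the seSBP and MAP comparisons outside the testing sequence. With a visit-to-visit seSBP correlation of 0.5 to 0.7 and a systolic–diastolic correlation of 0.5, the central estimates are 13% to 25% more residual variance, and about three quarters of a chance systolic imbalance effect is left uncorrected. When both correlations are 0.8 the precision loss is 4% or nil.

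A separate, low-impact point lies in SAP 15.3.3.3. Its model for target pressure in subjects with chronic kidney disease uses the double-blind treatment factor, which includes losartan, at Week 8 as well as Week 6. The Week 8 model then has no placebo level and gives no AZM versus placebo odds ratio. The subgroup analyses in 7.5 cover this comparison for the 90th percentile target but not for the 50th. Protocol 13.1.3 only tabulates these targets. Section 15.3.3.3 also models observed data where 15.3.2.3 specifies last observation carried forward, so its planned observed-data sensitivity analysis would repeat the main one.

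**What to change.** Before the Withdrawal-Phase database is unblinded:

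- In SAP 15.2.3.1, name the covariate as the Week 6/Final Visit seSBP of the double-blind phase for the seSBP model, and the MAP at the same visit for the MAP model.
- Add both to the list in 7.1, beside the Week 6 seDBP already there.
- In 6.3, replace seDBP by seSBP in the first secondary endpoint.

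As a lesser item, split the kidney-disease sentence in 15.3.3.3 by visit. Keep the factor with losartan at Week 6. At Week 8, either tabulate by Withdrawal-Phase treatment, as protocol 13.1.3 does, or use the factor with placebo and exclude subjects given losartan in the double-blind phase. Tabulation may be enough. If 20% of 213 subjects had kidney disease (an assumption), 213 × 0.20 × 0.75 / 2 / 3 ≈ 5 per AZM dose would still be on drug at Week 8, before dropout. Reconcile the data set named in both model sentences of 15.3.3.3 with 15.3.2.3.

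The cost is SAP wording only. All the values are already collected.

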A logistic model with treatment, age and weight as fixed effects and baseline clinic BP as covariate will be used to analyze the percent of subjects achieving target BP at Week 8/Final Visit of the Withdrawal Phase. The odds ratio and associated 95% confidence interval (CI) will be estimated. Similar logistic regression may be performed on percent of subjects achieving target BP at Week 6/Final Visit of the DB Phase. The target blood pressures (percentiles by age, gender and height) evaluated as secondary or additional endpoints include the following (at Week 6/Final Visit of the DB Phase and at Week 8/Final Visit of the Withdrawal Phase):

- seDBP <90th percentile.
- seSBP <90th percentile.
- Both seDBP<90th percentile and seSBP< 90th percentile.

Additional BP target endpoints to be tabulated (for seDBP, seSBP, and both) include:

- <90th percentile at Week 6/Final Visit of the DB Phase and Week 8/Final Visit of the Withdrawal Phase, for subjects with CKD.
- <50th percentile at Week 6/Final Visit of the DB Phase and Week 8/Final Visit of the Withdrawal Phase, for subjects with CKD.
- <90th percentile at Final Visit of OL Phase, for all subjects.
- <90th percentile at Final Visit of OL Phase, for subjects with CKD.
- <50th percentile at Final Visit of OL Phase, for subjects with CKD.

Descriptive statistics will be provided for the change from Baseline as well as the difference between each AZM treatment and losartan for 24-hour, 12-hour, daytime, night time, and trough ABPM SBP/DBP. Additional analysis of the SBP/DBP by ABPM will be performed where appropriate.

The efficacy analysis on DB Phase will be based on last-observation-carried-forward (LOCF) data set, unless otherwise specified. In the LOCF analysis data set, the last postbaseline double-blind observed value will be carried forward and used for all subsequent scheduled time points in the DB

Phase where data are missing (eg, the subject has missing data or has dropped out of the study). The efficacy analysis for the target BP will also be based on the LOCF data set. Sensitivity analyses on trough seDBP, seSBP, and MAP will be performed on observed values and using multiple imputation for missing trough BP data to assess the impact of LOCF methodology and drop-outs.

Subgroup analyses such as gender, race, region, diagnosis (primary versus secondary hypertension), and other important baseline factors may be performed on the primary endpoint and secondary endpoints as appropriate.

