3. STUDY DESIGN

3.1. GENERAL DESCRIPTION

AR14.001 is a global phase 3, efficacy and safety study of AZM in children aged 6 to <18 years with primary or secondary hypertension. Approximately 260 subjects will participate in a 6- week, double-blind (DB), randomized, treatment phase (DB Phase), followed by a 2 week, double-blind, randomized placebo-controlled withdrawal (Withdrawal Phase). In the DB Phase, subjects will be randomized (1:1:1:1) to 1 of 4 treatment arms AZM (low [AZM-L], intermediate [AZM-M] or high [AZM-H]) using 4 doses (10, 20, 40, and 80 mg) or losartan. The dose of AZM or losartan used will be dependent on the subject's weight. In the Withdrawal Phase, subjects will be randomized (1:1) to continue taking their previously assigned active treatment or to be switched to placebo. In the Withdrawal Phase, subjects will be randomized (1:1) to continue taking their previously assigned active treatment or to be switched to placebo.

This study also includes a 44-week, Open-label extension (OL Phase) in which all subjects will receive AZM and other antihypertensive medications (if needed) according to a titrate-to-target blood pressure (BP) algorithm. The study will be conducted at approximately 120 sites. BP will be assessed in the clinic throughout the study, and subjects may also participate in a 24-hour ambulatory blood pressure monitoring (ABPM) procedure at Baseline, at the end the DB Phase and at the end of the OL Phase.

Due to lower than expected standard deviation, the sample size was reduced to approximately 213 by Protocol Amendment 01 (Section 13.3).

Refer to Table A: Schematic of Study Design for an overview of the study design.

Document: 2014-000674-18 Statistical Analysis Plan Version 7.0 Version Number:

Template No.: CS_TP_BS016 Revision 5 Reference: CS_WI_BS005

Effective Date: 01Apr2018

Author:

Withdrawal **Double-Blind Phase** Pretreatment Phase Open-Label Phase AZM-H Placebo AZM-M М М Washout/ Placebo Run-in AZM + Others(s) Placebo (Titrate-to-Target BP) AZM-L AZM-L Placebo Losartan 50/100 50/100 → 50/100 25/50 Placebo RZ RZ Titration D-28 D-14 W4 W6 W8 W12 W20 W28 W36 W52 W54 D1 W2 (a) (c) ABPM ABPM ABPM ABPM ABPM ABPM removal fitting fitting fitting removal (W6-1D) (W52-1D)

Table A: Schematic of Study Design

AZM-L=low-dose AZM, AZM-M=intermediate-dose AZM, AZM-H=high-dose AZM, RZ=Randomization, D=Day, W=Week.

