3.2. RANDOMIZATION

The investigator or investigator's designee will access the interactive (voice/web) response system (IVRS/IWRS) at Screening to obtain the subject's study number. The investigator or the investigator's designee will utilize the IVRS/IWRS to enter the subject into the Placebo Run-in Phase. The IVRS/IWRS will also be used to randomize the subject into the DB Phase and later the Withdrawal Phase. The DB Phase

Document: 2014-000674-18 Statistical Analysis Plan Version 7.0 Version Number: 7.0

Author: Version Date: 13JAN2020

Template No.: CS_TP_BS016 Revision 5 Reference: CS_WI_BS005

Effective Date: 01Apr2018

randomization will be stratified by age (Tanner stage <3, ≥3), weight (≥25 to <50 kg, ≥50 kg), and race (non-Black, Black).

Enrolment caps will also be applied to randomization to ensure a percentage of subjects with secondary hypertension of approximately 40%-60% and to ensure that no more than \approx 25% of subjects are post-renal transplant subjects and no more than \approx 60% of subjects weigh greater than or equal to 50 kg at Baseline. Randomization for the Withdrawal Phase will be stratified by the treatment received in the DB Phase (i.e., AZM-L, AZM-M, or AZM-H or losartan).

Protocol Amendment 01, dated 12 Dec 2018, revised the number of secondary hypertensive subjects and < 50 kg subjects due to difficulty in recruiting these subpopulations. The expected number of secondary hypertensive subjects and subjects weighing less than 50 kg was not achieved. The revised expected percentage of subjects with secondary hypertension and subjects weighing less than 50 kg will be at least 20% of the total subject population.

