9. DISPOSITION AND WITHDRAWALS

All subjects who provide informed consent will be accounted for in this study.

The number and percentage of subjects in each disposition category will be presented; there will be no inferential analysis of subject disposition data.

Disposition of all enrolled but not randomized subjects will be tabulated according to screen failure/run-in failure, including primary reason for screen/run-in failure (pretreatment event, major protocol deviation, lost to follow-up, voluntary withdrawal, study termination, did not meet entrance criteria, other) as entered on the electronic case report form (eCRF).

Disposition of all randomized subjects will be tabulated by study phase, treatment group, pooled AZM (for DB and Withdrawal phases only) and overall. Treatments for DB phase are Losartan, AZM low dose, AZM intermediate dose, AZM high dose. Treatments for Withdrawal phase are Placebo, Losartan, AZM low dose, AZM intermediate dose, AZM high dose. Treatments for OL phase are AZM alone, AZM plus additional antihypertensive.

Primary reasons for discontinuation of study drug/visits, as entered on the eCRF, will be tabulated by phase and treatment group; the reasons include adverse event, major protocol deviation, lost to follow-up, voluntary withdrawal, study termination, pregnancy, lack of efficacy, PI discretion and other.

Major protocol deviations will be summarized for RND by phase, treatment group, pooled AZM (for DB and Withdrawal phases only) and overall. Protocol deviations will be presented in a data listing. Also, violation of Inclusion/Exclusion criteria will be listed for RND.

The number of subjects included in each analysis population will be summarized by phase, treatment group, pooled AZM (for DB and Withdrawal phases only) and overall.

Subject disposition, study discontinuation and study visit dates and times will be listed based on RND.

Document: 2014-000674-18 Statistical Analysis Plan Version 7.0 Version Number: 7.0

Version Date:

13JAN2020

Township No. 00 TB B0040 Building 5

Template No.: CS_TP_BS016 Revision 5 Reference: CS_WI_BS005

Effective Date: 01Apr2018

Author:

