15.1.3. Primary Analysis of Primary Efficacy Variable(s)

The primary objective of this study is to evaluate the antihypertensive effect of AZM compared with placebo after a randomized, double-blind, withdrawal (Withdrawal Phase).

The primary efficacy analysis will be performed for the FAS. The primary analysis will exclude subjects that were treated with losartan during the DB Phase.

The primary efficacy variable analysis will be an ANCOVA model with treatment (AZM low, med, high and placebo), age (Tanner stage <3, ≥3), race (Black or African American, Non- Black or African American) and weight (<50 kg, ≥50 kg) as fixed effects, and Week 6/Final Visit of the DB Phase seDBP as a covariate. The primary comparison, mean (i.e. pooled) AZM effect versus placebo, will be made using an ANCOVA contrast statement. Comparisons between each AZM dose to placebo will also be done from the framework of the above ANCOVA using contrast statements.

To control for multiplicity of the type 1 error, the sequential testing procedure mentioned in Section 7.4 will be employed in the analysis of the primary endpoint.

Summary of observed seDBP at Week 6 and Week 8 will be presented. Change in seDBP from Week 6 to Week 8 and the results from the analysis (Least square (LS) means, Standard Error, LS Mean Difference (SE), P-value and 95% Confidence Interval for Difference in LS means) will also be presented.

Profile plots (line with symbol at each visit with +/- 1 SE error bars) will be displayed for observed seDBP and boxplot will be displayed for the change in seDBP from Week 6 to Week 8.

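### SAP 15.2.3.3 omits the losartan exclusion, so read literally about a quarter of the placebo group in the Week 8 target-BP analysis was withdrawn from losartan rather than AZM

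*SAP*

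**What the plan says.** Three Withdrawal Phase analyses in the SAP use one treatment factor with four levels: AZM low, AZM medium, AZM high and placebo.

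- SAP 15.1.3, primary endpoint (seDBP change): "The primary analysis will exclude subjects that were treated with losartan during the DB Phase".
- SAP 15.2.3.1, seSBP and MAP change: "This analysis will exclude subjects that were treated with losartan during the DB Phase".
- SAP 15.2.3.3, BP below the 90th percentile at Week 8: "conducted using logistic models with treatment (AZM low, med, high and placebo", with no exclusion stated.

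Protocol 13.1.3 states the losartan exclusion for the primary analysis. For the responder endpoint it gives only "A logistic model with treatment, age and weight as fixed effects and baseline clinic BP as covariate", with neither treatment levels nor an exclusion.

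Four other provisions decide who enters the model:

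- SAP 15.2 runs the secondary efficacy analyses on the FAS. SAP 5.3 defines the FAS separately for each phase, as every child randomised and dosed in that phase, analysed as randomised.
- SAP 9 has a single placebo group for the phase: "Treatments for Withdrawal phase are Placebo, Losartan, AZM low dose" and the two higher AZM doses. The treatment-group table in SAP Appendix 1 does the same.
- SAP 3.1: "In the Withdrawal Phase, subjects will be randomized (1:1) to continue taking their previously assigned active treatment or to be switched to placebo".
- SAP 3.2: "Randomization for the Withdrawal Phase will be stratified by the treatment received in the DB Phase", with losartan as one of the strata.

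**The concern.** Because re-randomisation is stratified by DB treatment, each stratum is its own randomised withdrawal experiment. In the losartan stratum the randomised contrast is continued losartan against placebo. On the wording of 15.2.3.3, children who continue losartan match no treatment level and leave the model, while those switched to placebo match the placebo level and stay. Half of a randomised pair is kept and set against a drug those children did not receive.

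Three consequences follow.

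1. The comparator mixes two things, stopping AZM and stopping losartan. Responder status is an absolute BP level at Week 8, so any difference between the drugs in Week 6 control, or in how fast BP returns, carries into the odds ratio.
2. The model has little protection against this. Its covariate is baseline clinic BP, and the default in SAP 6.2 is the last value before first dose. The primary analysis both adjusts for Week 6 seDBP and excludes the losartan children.
3. The seDBP, seSBP and MAP changes would be reported against one placebo group and the responder rates against another, under the same label. SAP 7.5 asks for pooled AZM versus placebo p-values by subgroup for the secondary endpoints, so the mismatch would recur there.

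**Working it through.** **The plan's own figure.** The documents give no sample size or power for the responder endpoint. The nearest stated figure is the revised power for the primary endpoint (SAP 3.5): 52 per arm, 10% dropout, SD 8.3 mm Hg, difference 4.5 mm Hg, two-sided 0.05, power above 80%.

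- AZM completers: 3 × 52 × 0.9 = 140.4, or 70.2 per group after 1:1 re-randomisation.
- Power = Φ(4.5 / (8.3 × √(2/70.2)) − 1.96) = Φ(3.21 − 1.96) = 89.5%; 89.1% with the noncentral t.

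This agrees with the stated figure and uses AZM-treated children only. The primary comparison does not need the losartan children.

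**Who is in the placebo level.** Inputs: "In the DB Phase, subjects will be randomized (1:1:1:1) to 1 of 4 treatment arms" (SAP 3.1), then 1:1 within each DB treatment, with 52 per arm.

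- To placebo from each DB arm: 52 / 2 = 26.
- Placebo as 15.2.3.3 is written: 4 × 26 = 104.
- Placebo with the exclusion: 3 × 26 = 78.
- Share from losartan: 26 / 104 = 25.0%.

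| Case | Placebo, all | From losartan | Share |
|---|---|---|---|
| As randomised, N = 208 | 104 | 26 | 25.0% |
| Equal 10% dropout | 93.6 | 23.4 | 25.0% |
| No losartan dropout, 10% overall (assumed) | 93.6 | 26.0 | 27.8% |
| 20% losartan dropout, 10% overall (assumed) | 93.6 | 20.8 | 22.2% |

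With the protocol's minimum of 213 children, placebo falls from 213 / 2 = 106.5 to 0.75 × 106.5 = 79.9; the share is unchanged.

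**Direction and size of the effect.** The documents give no responder rates, so these are assumed for illustration: 60% at target on continued AZM and 40% on AZM-to-placebo.

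- AZM-origin placebo only: OR = (0.60/0.40) / (0.40/0.60) = 2.25.
- Losartan-to-placebo at 30%: pooled placebo = 0.75 × 40 + 0.25 × 30 = 37.5%; OR = 1.5 / 0.600 = 2.50.
- Losartan-to-placebo at 50%: pooled placebo = 0.75 × 40 + 0.25 × 50 = 42.5%; OR = 1.5 / 0.739 = 2.03.
- Losartan-to-placebo at 40%: no change.

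**Against sampling error.** With 78 AZM children at 60% and 104 placebo at 40%, SE(log OR) = √(1/46.8 + 1/31.2 + 1/41.6 + 1/62.4) = 0.31. The 95% interval around 2.25 is about 1.2 to 4.1. The shift, ln(2.50/2.25) = 0.105, is about a third of one SE. For a single AZM dose (26 children) the SE is √(1/15.6 + 1/10.4 + 1/41.6 + 1/62.4) = 0.45, and the same shift is under a quarter of it.

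**Precision given up by excluding.** At the same assumed rates with 78 placebo children, the pooled SE is √(1/46.8 + 1/31.2 + 1/31.2 + 1/46.8) = 0.33 against 0.31. For a single dose it is √(1/15.6 + 1/10.4 + 1/31.2 + 1/46.8) = 0.46 against 0.45.

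**The case against.** **Inclusion is inferred.** No sentence says that losartan-to-placebo children enter this model. SAP 7.1 lists one Withdrawal Phase treatment factor, and in 15.1.3 and 15.2.3.1 its placebo level already leaves these children out, so a programmer could reuse that dataset. SAP 9 describes disposition tables, and its single placebo label coexists with the exclusion elsewhere. The output templates mentioned in SAP 8 are not among the documents and might state the restriction. This stands as a limit on certainty: the text is silent, and inclusion follows from the FAS definition and the level list. It does not remove the point. The authors added an explicit exclusion twice beside the same level list, and the sentence in 15.2.3.1 is confined to that analysis.

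**The covariate may be Week 6 BP.** SAP Appendix 1 says Visit 8 data serve as the Withdrawal Phase baseline, which could be read into 15.2.3.3. Against that, SAP 7.1 lists Week 6 seDBP separately from baseline seDBP, and 15.2.3.3 says only baseline. The lack of Week 6 adjustment therefore rests on the default definition. A Week 6 covariate would reduce the problem but leave the mixed comparator in place.

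**The effect may be small.** The illustrated shift needs a 10-point gap between the two placebo sources, is small against the standard error, and uses a pooled odds ratio that 15.2.3.3 does not itself specify. All of that stands.

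**A stronger reading to avoid.** A reader might infer that a quarter of the placebo group was never randomised against AZM. The documents do not support that: every child was randomised at Day 1 among three AZM arms and losartan. What is missing is re-randomisation against AZM in the Withdrawal Phase.

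**Conclusion.** The omission is real and more than a missing detail, because following the text as written gives the wrong comparator. On that reading about 26 of 104 placebo children (25%; 22% to 28% under the unequal dropout assumed above) came from losartan, while their randomised partners are left out. The count assumes 52 per arm and the stated allocation ratios.

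The direction of any bias cannot be predicted. Its size is unknown because the documents give no responder rates; the odds ratios above are illustrations only.

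A reader might also infer that the trial's main conclusion is exposed. It is not. The primary analysis and the seSBP and MAP analyses carry the exclusion, the primary power is unchanged, and the sequential procedure in SAP 7.4 covers only the primary endpoint. This is a secondary-endpoint correction that should be made before unblinding.

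**What to change.** Add to SAP 15.2.3.3 the sentence already in 15.2.3.1: "This analysis will exclude subjects that were treated with losartan during the DB Phase". State that it also applies to the multiple-imputation sensitivity analysis of this endpoint and to its AZM-versus-placebo subgroup runs under SAP 7.5. If a placebo group pooled across AZM and losartan origin was intended, say so and justify it.

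Responder rates for continued losartan and losartan-to-placebo could be shown descriptively in separate columns, but this is optional.

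The cost is one sentence. The placebo group in this model falls from about 104 to about 78, with the slightly wider interval shown in the working. In return, the responder result rests on the same children as the primary analysis.
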